9.11. Follow Up

Follow up visits/procedures after specific clinical outcomes (HCC diagnosis/liver transplant and death)

HCC Diagnosis

If a diagnosis of HCC is made during the study, no further in person follow up visits or nceMRI scans will take place. Follow up data will continue to be collected at 6 monthly intervals from hospital records.

Liver Transplant

If a participant receives a liver transplant during the study, no further in person follow up visits or nceMRI scans will take place. Follow up data will continue to be collected at 6 monthly intervals from hospital records.

Death

If a participant dies, the date and cause of death should be clearly documented using the 'Mortality' form within REDCap. In the event that a participant's death certificate is not available on hospital records, the local study team may be asked to contact the relevant GP to obtain date/cause of death data.

Long-Term Follow-up

The study teams will obtain data from NHS England, the NHS Central Register for Scotland and other patient registries on participants for up to 10 years after the last follow-up visit, phone call or email. This will be a passive follow-up with no participant involvement.

9.12. Sample Handling

Blood or other biological samples will not be collected from participants.

9.13. Early Discontinuation/Withdrawal of Participants

During the course of the study a participant may choose to withdraw early from the study at any time. This may happen for several reasons, including but not limited to:

- The occurrence of what the participant perceives as an intolerable AE.
- Inability to comply with study procedures
- Participant decision

Participants may choose to stop study assessments but may remain on study follow-up.

Participants may also withdraw their consent, meaning that they wish to withdraw from the study completely. In the case of withdrawal before completing the 30 months of study participation and without completing the 6 research visits, the following options for a tiered withdrawal from the study will be available to participants:

 Participants may withdraw from further research visits, and further communication but allow the study team to continue to access their medical records and any relevant hospital data that is recorded as part of routine standard of care; e.g., scans, blood results and disease progression data etc.

- 2) Participants can withdraw from the study but permit data obtained up until the point of withdrawal to be retained for use in the study analysis. No further data would be collected after withdrawal.
- 3) Participants can withdraw completely from the study and withdraw the data collected up until the point of withdrawal. The data already collected would not be used in the final study analysis.

In addition, the Investigator may discontinue a participant from the study MRI procedures at any time if the Investigator considers it necessary for any reason including, but not limited to:

- Pregnancy
- Ineligibility (either arising during the study or retrospectively having been overlooked at screening)
- Significant protocol deviation
- Significant non-compliance with the study requirements Clinical decision (e.g. patient no longer suitable for ongoing surveillance)

Participants who withdraw will not be replaced as the sample calculation already allows for attrition.

The type of withdrawal and reason for withdrawal will be recorded in the CRF.

If the participant is withdrawn due to disease progression or an adverse event, the Investigator will arrange for follow-up visits or telephone calls until the adverse event has resolved or the participants condition optimised.

Procedures to minimise attrition

Attrition may result due to patients not returning for follow-up visits, or progression of liver disease to Child Pugh stage C or other comorbidities such that surveillance is no longer indicated. To avoid attrition from missed scans, we plan to call participants within two weeks prior to their appointment to remind them of their upcoming visit and participants will be reimbursed for travel and food. To avoid attrition from liver disease decompensation, sites will be asked to manage patients according to National guidelines¹⁰.

9.14. Definition of End of Study

The end of the study from a participant perspective will be month 30 (visit 6). The end of study will be the date of the final analysis of the data of the last participant.

10. SAFETY REPORTING

This is not an interventional study, but MRI scanning can have potential side effects.For this reason, data on serious adverse events (SAE) relating to the MRI procedures (ceMRI and nceMRI) will be collected in the SAE report form.

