5.5. Potential risks and benefits

If MRI is superior to USS for HCC surveillance participants may benefit from diagnosis of HCC at an earlier stage, which in turn can lead to more effective treatment and better survival.

The main risk to participants will be risks related to false positive results that may lead to unnecessary anxiety, added investigations and possible invasive procedures. The risk of suffering harm during the MRI examination is minimised through safety screening which will be repeated before each scanning session.

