7. STUDY DESIGN

This will be a single-arm, multi-centre, prospective cohort study evaluating the diagnostic accuracy of nceMRI and USS for diagnosis of HCC in people at high risk of HCC. People at high risk of HCC include those with liver cirrhosis and a high risk of HCC, or those with previous successfully treated HCC who are back in surveillance with USS. Participants will be recruited from UK hospital-based liver clinics over a period of 18 months and study procedures will take place in UK hospitals and academic centres. Participants will undergo 6 rounds of 6 monthly surveillance with nceMRI and USS over 30 months. Participants will be invited to complete questionnaires at each study visit. Relevant data will also be extracted from the participants' medical records. If at any surveillance round, a surveillance test raises a concern for the presence of HCC, participants will undergo full diagnostic contrast enhanced MRI (ceMRI) to determine whether HCC is present or not. In cases where indeterminate lesions for HCC are reported, these may require further tests including contrast CT, follow-up contrast enhanced MRI, or biopsy as directed by the clinical team. All participants will undergo diagnostic full contrast enhanced MRI at the end of their study participation. If an HCC is diagnosed at any point in the study, then participants will receive treatment according to standard clinical protocols as part of standard of care.

Long-term follow up of medical records from NHS England, the NHS Central Register for Scotland and other patient registries may be conducted for up to 10 years after the end of the active follow up phase. Data obtained from these registries will include but is not limited to liver disease, decompensation episodes, HCC diagnosis, liver transplantation and death. There will be no additional involvement from study sites or participants, as the long-term follow up only involves accessing centrally held medical data.

The overall study design and participant flow is summarised in Figure 1.

Figure 1: AMULET study design and patient flow

Abbreviations: HCC: hepatocellular cancer; USS: ultrasound scan; nceMRI: non-contrast enhanced MRI; AFP: alpha-fetoprotein; HADS: hospital anxiety and depression scale; +ve: positive; -ve: negative [#] see section 9.4 for the description of the procedure for HCC risk estimation

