9.8.1. Description of comparator(s)

The comparator will be the diagnosis of hepatocellular carcinoma based on the typical features on contrast enhanced MRI or CT or histological diagnosis (biopsy or resection) or a consensus diagnosis of HCC as determined by the local MDT will be accepted as a diagnosis of HCC.

On study contrast enhanced MRI scans

For cases where a contrast enhanced MR is done following a positive surveillance test (on study ceMRI), lesions classified as LI-RADS 1 or 2 will be regarded as negative for HCC and lesions classified as LI-RADS 5 will be regarded as positive for HCC. Lesions classified as LI-RADS 3 or 4 will be regarded as indeterminate and will be followed up according to the local clinical routine. If LI-RADS 3 or 4 are designated as HCC by the local MDT, or they are proven to be HCC on biopsy, or they progress to LI-RADS 5 within the 30 months of follow-up then they will be defined as HCC for the analysis relating to the whole 30 month period of surveillance. In cases where LI-RADS 3 or 4 lesions remain under follow-up at the end of the 30 months follow-up without a clear classification as HCC or benign, or where they have been histologically proven to be benign, then they will be classified as negative for HCC for the purposes of the analysis. The classification of lesions at on-study ceMRI scans is shown below in Figure 2. The follow-up of LI-RADS 3 and 4 lesions in this situation will finish at the timepoint that visit 6 was due or at an earlier time point if a definitive classification is reached before then.

Figure 2: Flowchart for the classification of lesions detected on contrast enhanced MRI performed during the study following a positive surveillance test. In cases where lesions are determined as negative within the 30-month surveillance period, participants will re-enter the AMULET surveillance schedule until they complete the study. Where a positive for HCC diagnosis is made, participants will end their participation, will undergo no further surveillance and will be managed according to the recommendations of the local MDT. Participants with LI-RADS 3 or 4 lesions who are undergoing interval contrast enhanced imaging as recommended by the local MDT will be suspended from participation in AMULET.

End of Study contrast enhanced MRI scan

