10.3. Reporting Procedures for Serious Adverse Events

A serious adverse event (SAE) occurring to a participant should be reported to the REC that gave a favourable opinion of the study where in the opinion of the Chief Investigator the event was 'related' (resulted from administration of any of the research procedures) and 'unexpected' in relation to those procedures. Reports of related and unexpected SAEs should be submitted within 15 working days of the Chief Investigator becoming aware of the event, using the HRA report of serious adverse event form (see HRA website).

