13.3. Study Committees

Study Management Group

A Study Management Group (SMG) will provide day-to-day management of the study. The SMG group will include the study investigators, PPI representatives and the study project managers. The SMG will convene at least monthly during the first 2.5 years of the project (either face-to-face or via teleconference), then 2-3 monthly thereafter. Extended SMG meetings to include investigators from each of the recruiting sites will be convened as required within this schedule. The SMG will be further structured in the following themes to have oversight of different aspects of the study:

- 1. Study Governance, Recruitment and PPI
- 2. Radiology and USS

- 3. MRI set-up and mechanistic sub study
- 4. Data and analytics

Project Steering Committee

A Project Steering Committee (PSC) will be established and will have overall responsibility for the conduct of the study. The PSC will consist of 8 members (6 independent, 2 study investigators). The 6 independent members will include an independent chair, a PPI representative and 4 members with expertise relevant to the trial (hepatology, radiology, MRI physics, epidemiology / statistics). The PSC will meet at least annually. Additional meetings will be organised as needed at the request of the chair or the CI. Observers from relevant stakeholders including the investigators, sponsor, study funder and patient support organisations will be invited to attend PSC meeting.

Data Monitoring and Ethics Committee

A Data Monitoring and Ethics Committee (DMEC) will be established and will have oversight of primary data collected from participants and to uphold the safety, rights and well-being of the participants. The DMEC will consist of 3-4 members all of whom will be independent with expertise relevant to the trial (hepatology, radiology, MRI physics, epidemiology / statistics). The DMEC will meet at least annually. Additional meetings will be organised as needed at the request of the chair or the CI. The primary DMEC reporting line is via the Chair to the Steering Committee.

PPI Advisory Group

A PPI advisory group that includes the PPI co-applicant, PPI coordinator, and PPI representatives from the Hepatitis C Trust, Haemochromatosis UK, British Liver Trust has been established. This group will act as a conduit between the SMG, PSC and the wider PPI membership.

The PPI advisory group will provide insight and advice on:

- study design

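### Section 10 collects only MRI-related SAEs, so serious complications of CT, biopsy or other invasive work-up prompted by a study scan have no clear capture route

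*Protocol*

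**What the plan says.** The protocol's own statement of risk is in section 5.5: "The main risk to participants will be risks related to false positive results that may lead to unnecessary anxiety, added investigations and possible invasive procedures".

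Section 7 describes what can follow when a lesion is indeterminate: "these may require further tests including contrast CT, follow-up contrast enhanced MRI, or biopsy as directed by the clinical team".

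Section 10 gives the side effects of MRI as its reason for collecting safety data and sets the scope accordingly: "data on serious adverse events (SAE) relating to the MRI procedures (ceMRI and nceMRI) will be collected in the SAE report form". Section 10.3 deals with onward reporting to the ethics committee. It covers unexpected events that are also related, a related event being one that "resulted from administration of any of the research procedures".

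Three other places bear on capture:

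- Appendix A has a row for adverse event assessments and a row for case-notes review, both marked at baseline and at visits 2 to 6. Neither says which events are in scope, and no column follows visit 6.
- Section 9.8.1 states: "Participants with LI-RADS 3 or 4 lesions who are undergoing interval contrast enhanced imaging as recommended by the local MDT will be suspended from participation".
- Section 9.10 puts a contrast MRI at visit 6 for all participants. Section 9.14 ends participation at that visit, and section 9.11 leaves only passive registry follow-up afterwards.

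**The concern.** The risk that the protocol ranks first and the safety data that it collects do not match. A serious bleed after a biopsy is not an MRI event in the ordinary sense of section 10. Because the clinical team directs the work-up, it is also not clearly the result of administering a research procedure under section 10.3.

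The harm can still be attributable to the study. Ultrasound is routine care, whereas nceMRI is added by AMULET, so work-up of a false positive seen only on nceMRI would not have happened outside the study. At stake is whether the final report can say anything about serious harm from that work-up, by modality or at all.

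**Working it through.** No stated figure is at issue, so the main check sets each possible capture route beside the gap.

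| Route | Does it capture a serious complication of CT or biopsy? |
|---|---|
| SAE form (section 10) | Not on its wording, which is confined to nceMRI and ceMRI. |
| Reporting to the ethics committee (10.3) | Unclear. It governs onward reporting rather than collection, and turns on administration of a research procedure. |
| Adverse event row (Appendix A) | Possibly, at the next visit. Its scope is unstated and it is not reconciled with section 10. |
| Case-notes review (Appendix A) | It could find the event, but nothing says that such an event is then recorded as safety data. |
| Six-monthly record collection (9.11) | Only after an HCC diagnosis or a liver transplant, so not for false positives. |
| Adverse event follow-up (9.13) | Only for participants withdrawn for disease progression or an adverse event. |
| Follow-up of an SAE to its end (10.2) | Only once the event is already known. |
| Death form (9.11) | Deaths only, with date and cause. |
| HADS and EQ-5D-5L (11.2) | The anxiety and quality-of-life part of the risk only. |

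Two groups have less chance of being picked up at a visit. Participants on interval imaging for LI-RADS 3 or 4 lesions are suspended while that imaging goes on. For those reaching visit 6, any event that starts after the final contrast MRI, or after work-up which that scan prompts, falls beyond the last scheduled contact. Section 9.8.1 itself notes that LI-RADS 3 and 4 lesions found on the end-of-study scan cannot be followed up within the study.

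The scale of false positives follows from section 11.3. Inputs: assumed specificity 80% for nceMRI and 90% for ultrasound; about 250 to 300 controls without HCC. Section 11.2 gives each test one diagnostic category per participant over the 30 months, so specificity is taken per participant.

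Expected false-positive participants = controls × (1 − specificity):

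- nceMRI: 250 × 0.20 = 50; 300 × 0.20 = 60.
- Ultrasound: 250 × 0.10 = 25; 300 × 0.10 = 30.

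Participants with a false positive on either test depend on how far the two overlap, which the protocol does not state:

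- Full overlap: 50 to 60.
- Independent: 250 × (1 − 0.80 × 0.90) = 250 × 0.28 = 70; 300 × 0.28 = 84.
- No overlap: 50 + 25 = 75; 60 + 30 = 90.

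These are counts of false-positive participants, not of people who have a CT or biopsy. Many would end at a contrast MRI read as LI-RADS 1 or 2. The protocol gives no share proceeding further, so the number exposed to harm outside the SAE scope cannot be derived.

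**The case against.** The strongest reply is that this is a deliberate scope with a stated reason. The study is described as non-interventional, the clinical team directs work-up, and SAE collection is limited to the scans that the study adds. Much of the section 5.5 risk is also measured. Contrast MRI, the first investigation after any positive test, is inside the SAE scope. HADS and EQ-5D-5L are completed at every visit and explored against false-positive tests. False positives by modality are part of the primary outcome, and deaths are recorded with cause. The Appendix A rows carry no stated restriction, so a site might well record a biopsy complication at the next visit. Suspension is stated for interval imaging, not expressly for biopsy, and participants whose lesions prove negative return to the schedule.

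All of that stands, and it narrows the point to CT, biopsy and other invasive work-up. It does not close the gap, because no section says that these complications are to be collected.

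A reader might be tempted by stronger inferences that the documents do not support:

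- That all follow-up investigations go uncaptured. Contrast MRI is captured.
- That the benefit-harm conclusion will be biased towards nceMRI. No such conclusion is planned; the primary objective is diagnostic performance.
- That false positives should be counted by applying specificity to every scan over six rounds. Section 11.2 defines the categories per participant.
- That the monitoring committee will not see safety data. Section 13.3 gives it a safety remit, and the content of its listings is ordinary charter detail.
- That nothing but liver outcomes and death is available after visit 6. The registry list in section 7 is open-ended, and section 9.8.1 allows follow-up through medical records, although for lesion outcome and later HCC.

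**Conclusion.** The point holds in limited form. Serious complications of contrast CT, biopsy or other invasive work-up prompted by a study scan have no clear capture route, although section 5.5 places invasive procedures within the main risk. In addition, no participant contact is scheduled after the visit 6 contrast MRI. Section 9.10 gives that scan to everyone; section 9.8.1 describes it for those completing six rounds without a positive test or HCC, so the number affected depends on which text governs.

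On the protocol's specificities, read per participant, nceMRI would produce about twice as many false-positive participants as ultrasound (50 to 60 against 25 to 30). How many of them would have a CT or biopsy, and how many would be harmed, cannot be computed from the document. This is an inexpensive improvement to safety capture, not a flaw that threatens the primary analysis.

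**What to change.** Change data collection only; clinical management is not affected.

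1. In section 10, extend SAE collection to serious events arising from any CT, biopsy or other invasive procedure triggered by an on-study ultrasound, nceMRI or ceMRI finding. Record which modality triggered it.
2. State the scope of the adverse event row in Appendix A so that it agrees with section 10.
3. Name the case-notes review already in Appendix A as the means of finding these events, and state that it continues while a participant is suspended for a LI-RADS 3 or 4 lesion.
4. Add one closing record check after the visit 6 contrast MRI, at an interval that the sponsor specifies.

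The cost is protocol wording, one record check per participant reaching visit 6, and some extra SAE forms and causality assessments at sites.

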10.1. Definition of Serious Adverse Events

A serious adverse event is any untoward medical occurrence that:

- results in death
- is life-threatening
- requires inpatient hospitalisation or prolongation of existing hospitalisation
- results in persistent or significant disability/incapacity
- consists of a congenital anomaly or birth defect.

Other 'important medical events' may also be considered a serious adverse event when, based upon appropriate medical judgement, the event may jeopardise the participant and may require medical or surgical intervention to prevent one of the outcomes listed above.

NOTE: The term "life-threatening" in the definition of "serious" refers to an event in which the participant was at risk of death at the time of the event; it does not refer to an event which hypothetically might have caused death if it were more severe.

10.2. Follow-up of Serious Adverse Events

Any serious adverse event will be followed up until resolution or stabilisation.

10.3. Reporting Procedures for Serious Adverse Events

A serious adverse event (SAE) occurring to a participant should be reported to the REC that gave a favourable opinion of the study where in the opinion of the Chief Investigator the event was 'related' (resulted from administration of any of the research procedures) and 'unexpected' in relation to those procedures. Reports of related and unexpected SAEs should be submitted within 15 working days of the Chief Investigator becoming aware of the event, using the HRA report of serious adverse event form (see HRA website).

11. STATISTICS AND ANALYSIS

11.1. Statistical Analysis Plan (SAP)

The statistical aspects of the study are summarised here with details fully described in a statistical analysis plan that will be available from the time that the first participant is recruited. The SAP will be finalised before any analysis takes place.

11.2. Description of the Statistical Methods

Statistical analysis for Primary outcome measure

Measures of diagnostic performance will be determined per round of surveillance and over the 30 months of study participation.

Diagnostic performance per round of surveillance

At each round of surveillance, the following data will be calculated and compared between USS and nceMRI.

- 1. Number and proportions of positive surveillance USS and nceMRI see section 9 for definitions of positive tests
- Number and proportions of true positive (TP) and false positive (FP) USS and nceMRI. As each positive test will be followed by a full contrast enhanced MRI, TP and FP tests per round of surveillance will be calculated
- 3. Positive predictive value (PPV) of USS and nceMRI

Diagnostic performance for the overall study period of 30 months

For the purpose of this analysis, each USS and nceMRI scan for each participant completing the study will be assigned only one of the 4 possible diagnostic categories of: true positive (TP) or false positive (FP), true negative (TN) and false negative (FN). The sum of TP, FP, TN and FN in this analysis will therefore be equal to the total number of participants completing the study. TP and FP will be determined at each visit as described above. TN and FN will be determined at the end of the study when participants undergo the reference standard ceMRI as part of the study protocol. FN results will also include those cases that present with HCC during the study without a prior positive test (interval cancers) or cases where both USS and nceMRI are negative tests but a ceMRI scan is triggered by an AFP>20. Cases that are initially FP may subsequently change diagnostic category. For this analysis, the diagnostic category which is applicable at the end of the study will be used. For example, if a finding initially classed as an FP develops into an HCC that was correctly identified by the surveillance tests, then the diagnostic test will be counted as a TP for this analysis.

Sensitivity and specificity estimates will be calculated separately for nceMRI and USS and compared. Statistical significance of the observed differences in sensitivity/specificity will be evaluated using the McNemar's test of paired proportions, with a two-tailed P-value <0.05 used as the significance criteria.

Further, we will assess if specific individual-level factors are associated with the diagnostic performance of nceMRI and USS. These will include BMI, gender, age and underlying disease aetiology. For sensitivity, we will assess this by fitting a logistic regression model including all patients with HCC. The dependent variable will be detection via USS/nceMRI, whereas age/BMI and gender will be included as independent variables. Equivalent models will be fitted to determine factors associated with specificity, but this time confined to patients without HCC instead of patients with HCC. A further sensitivity analysis will be conducted in order to compare the sensitivity of nceMRI with USS depending on the USS visualisation scores.

Other considerations relevant to measuring the primary outcome

Alpha-fetoprotein

Alpha-fetoprotein will be measured as part of clinical care at each study visit. In the situation where both USS and nceMRI do not report suspicious lesions (test negative), a contrast enhanced MRI scan will still be needed if:

AFP \geq 20 ng/mL OR doubling of AFP (or more) OR increasing on two consecutive tests.

If an HCC is diagnosed on a ceMRI that was triggered by AFP thresholds rather than by USS / nceMRI, then both USS and nceMRI will be regarded as false negatives

Incidental findings:

Focal hepatic lesions: If an incidental finding is noted in the liver but no further imaging recommended (e.g. simple cysts), scans will be classed as test negative. Lesions in the liver, which are not thought to be HCC, but are considered to require imaging clarification with e.g. contrast-enhanced imaging, will be classed as test positive in the main study endpoint, but will be subject to a planned sensitivity analysis.

Cirrhosis-related complications: If a new ascites is identified on USS or MRI, this will be recorded (small, moderate and large volume). Other non-cancer complications of cirrhosis, such as development of features of portal hypertension, or venous thrombosis will be recorded for both tests.

Extrahepatic: Extrahepatic incidental findings will be documented on the study proforma and assessed for likely significance. If a significant incidental finding is noted outside the liver this will be documented. Subsequent follow-up investigations will be recorded, as well as any significant diagnoses. Incidental findings in organs outside the liver will be managed according to local clinical routine, and not be counted as TP or FP when calculating sensitivity and specificity of nceMRI/USS.

Statistical analyses for secondary outcome measures

- 1. At each surveillance round, graphical methods will be used to analyse data for the numbers of:
 - a. very early, early, intermediate and advanced stage HCC as defined by the Barcelona Clinic Liver Cancer Staging system
 - b. the size and number of HCC, in TP cases
 - c. The number of new indeterminate lesions
- 2. Graphical methods will be used to analyse data on the number and proportions of participants with HCC who receive treatment with curative intent.
- 3. Quality of life and anxiety and depression: QoL will be assessed using the EQ-5D-5L questionnaire and anxiety and depression using the Hospital Anxiety and Depression Scale (HADS). Patients will be asked to complete the questionnaires at 6 monthly intervals to coincide with their visits for MRI / USS. Associations of the results from these questionnaires with other variables will be explored, particularly with HCC diagnosis and FP surveillance tests.
- 4. Acceptability of MRI and USS as surveillance tests: Patients will be asked to complete questionnaires documenting their experience of USS and MRI at the baseline visit and visit 5. These questionnaires have already been developed based on the questionnaires used in the METRIC study⁴¹, which assessed the acceptability of USS and MRI in patients with Crohn's disease. Scores derived from these questionnaires will constitute the outcome measure and they will be compared between nceMRI and USS.
- 5. Feasibility of nceMRI and USS as surveillance tools: To measure feasibility of nceMRI and USS as a surveillance tool, data will be collected on the number and reasons for missed scans. In particular we will determine if scans were cancelled by the hospital due to capacity issues, if the patient was lost to follow-up, or surveillance for HCC is no longer indicated. This data will be analysed using graphical methods.
- 6. Multivariable algorithms: Demographic, laboratory and clinical data will be collected every 6 months including Child Pugh and Model for End-Stage Liver Disease (MELD) scores. Multivariate analysis will be used to assess if inclusion of nceMRI sequences and routinely available data or other biomarkers

improves diagnostic performance compared to USS. The multivariate models will be developed and reported according to the updated TRIPOD (Transparent Reporting of a multivariable prediction model for Individual Prognosis Or Diagnosis) statement⁴².

- 7. Mechanistic sub-study outcomes: Image processing of quantitative nceMRI and radiomics will be performed using semi-automated pipelines to study the "field effect". This will include:
 - a. automated liver segmentation using a convolution neural network, and manual definition of HCC;
 - b. creation of quantitative parameter maps from physical signal-models. We will perform model driven registration of DWI data to compute ADC and IVIM (D, D*, F) maps, quantify T1, R2*, and PDFF maps;
 - c. extraction of summary quantitative parameters and radiomics features in background liver parenchyma using a region growing algorithm progressively away from the defined HCC lesions
 - d. reporting the results in a standardised format and returning a table of imaging biomarkers for upload into the electronic data capture system.

